- Timing adherence: (Number of correct dosing intervals during 24 hours/number of dosing intervals during 24 hours) x100; correct dosing intervals are prescribed intervals $\pm 25\%$:
 - o For once daily dosing: $24h \pm 25\% = 18-30h$
 - o For twice daily dosing: $12h \pm 25\% = 9-15h$
 - o For three daily dosing: $8h \pm 25\% = 6-10h$
- Gaps: (Number of days without inhalation during the whole study period/number of days in same time period) x 100.
- Maximal gap length: Number of consecutive days of the longest period of time without inhalation.

Different lung function tests are performed at baseline, after two, four and six months to assess changes in lung function (FEV₁, FVC, FEV₁/FVC), diffusion capacity, NO-measurements and CO-measurements.

To evaluate the inhalation technique, participants demonstrate at baseline and at every follow up visit how they actually use their device at home. For this purpose, placebo devices are used to prevent overdosing. Correctness of inhaler use is assessed using pre-defined checklists for each inhaler type based on user guidelines and instruction package inserts from the manufacturers[50-55]. Correct inhaler usage is defined as correct performance of every step on the checklist. Incorrect inhaler usage is defined as one or more steps done incorrectly. A total score is calculated (incorrect application =0, correct application =1) and applied to every step. Possible errors are corrected by verbal instruction and visual demonstration. For ethical reasons the correction was performed in both groups. Patients demonstrate their inhalation technique until it is performed correctly.

To assess patients' beliefs about the need of the prescribed medication and their concerns about the potential adverse consequences of taking it, the BMQ is used at baseline.

Changes in quality of life are assessed at baseline, after two, four, six months using different disease-specific questionnaires: SGRQ, CAT and ACT. To assess general quality of life, SF-36-questionnaire is used.

STATISTICAL ANALYSIS

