Statistical analyses, including descriptive statistic and survival analyses, are done using the software R (RStudio®, Boston, USA) and SPSS (IBM Corporation, Armonk, USA). Statistical significance is set at the 5% level. Time to next exacerbation is compared using the Kaplan-Meier method and Cox proportional hazard model. Results will be reported as HR (hazard ratio) with corresponding 95% confidence interval (CI) and p-value. A hazard ratio smaller than one is expected. This means that the intervention group will have a smaller risk for exacerbations. Associations between time to between exacerbation and independent predictors will be analyzed (taking adherence, timing adherence and gaps without

inhalation). Comparisons of secondary parameters are done using t-tests or chi-square-tests (or their nonparametric equivalents if continuous data are not normally distributed).

HANDLING OF MISSING DATA AND DROP OUTS

Patients will be rated as drop out when they will be excluded from the study at their request or if they will be no longer able to participate in the study until the final visit at six months. Patients, who will not be able to undergo all clinical examination during the follow-up visits, will remain in the study. Multiple imputation methods will be used to impute missing data with less than 25% missing values, which is typically more efficient than complete cases analysis when covariates have missing values[56].

ETHICS AND DISSEMINATION

This study is conducted according to the Helsinki Declaration and according to the good clinical practice guidelines. The study participation of the patients is voluntary and can be revoked at any time without specification of reasons and will have no disadvantages for their future medical care. The study was approved by the Ethics Committee of Nordwest- and Zentralschweiz (registry number: EK- 269/13) and was registered in the <https://clinicaltrials.gov/trials> database (NCT02386722). The results of this study will be disseminated via seminar and conference presentations and in academic peer reviewed journals.

DATA SECURITY/DISCLOSURE OF ORIGINAL DOCUMENTS

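### Timing adherence and gaps depend on prescribed dosing frequency for the same behaviour, and the plan neither adjusts for frequency nor reports by it; arm comparisons stay valid, but the exploratory link to exacerbation could be confounded.

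*Combined protocol and SAP*

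**What the plan says.** Data collection and outcome measures defines timing adherence as "Number of correct dosing intervals during 24 hours/number of dosing intervals during 24 hours", times 100, where "correct dosing intervals are prescribed intervals" plus or minus 25%. It lists windows of 18–30 h, 9–15 h and 6–10 h for once-, twice- and three-times-daily dosing. Gaps are "Number of days without inhalation during the whole study period/number of days in same time period", times 100, and maximal gap length is the longest run of such days. Taking adherence, by contrast, divides puffs inhaled by puffs prescribed, so it is already scaled to the regimen.

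Statistical analysis states: "Comparisons of secondary parameters are done using t-tests or chi-square-tests", with nonparametric equivalents for non-normal data. It also says that associations between time to exacerbation and "independent predictors will be analyzed (taking adherence, timing adherence and gaps without" (inhalation) will be examined. No section names adjustment, stratification or separate reporting by dosing frequency, or a rule for patients with several inhalers. Pooling is not stated in words. It follows from this silence and from the choice of two-sample tests.

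Three further facts matter. Treating physicians decide all prescriptions (Study design and procedures). Randomisation uses blocks of two, with no stratification named (Randomization). Current medication is recorded at baseline (Data collection and outcome measures).

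**The concern.** A proportional window narrows in hours as doses become more frequent, so the same irregularity by the clock costs a twice-daily user more than a once-daily user. Gaps work the other way: a day counts only if every dose is missed, so a once-daily user who misses the same fraction of doses collects far more gap days. Patients who behave alike look better or worse according to what they were prescribed.

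Two analyses use these scores. In the arm comparison, differences between regimens add variance, and a chance imbalance in regimen goes uncorrected. In the association with exacerbation, adherence is not randomised and the physician chooses the regimen. If regimen is related to risk, timing adherence and gaps could appear to predict exacerbation because they carry information about the regimen. Adherence is part of the stated study objective and the route by which the intervention is expected to work, so these secondary results will be read closely.

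**Working it through.** **The plan's own figures.** 24 h × (1 ± 0.25) = 18–30 h; 12 h × (1 ± 0.25) = 9–15 h; 8 h × (1 ± 0.25) = 6–10 h. All three windows reproduce. The half-widths are w = 6, 3 and 2 h.

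The documents give no dose-time variability, miss rate, regimen mix or regimen effect on risk. Every such value below is an assumption.

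**Timing adherence, no dose missed.** Let s be the SD of a dose time around its schedule. The interval between two doses then has SD s√2, and P(correct) = 2Φ(w/(s√2)) − 1.

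| s | once | twice | three times |
|---|---|---|---|
| 1 h | 100% | 97% | 84% |
| 1.5 h | 99.5% | 84% | 65% |
| 2 h | 97% | 71% | 52% |
| 3 h | 84% | 52% | 36% |

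**Gaps.** With miss probability q per dose, k doses a day and independent misses, the expected gap fraction is q^k.

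| q | once | twice | three times |
|---|---|---|---|
| 10% | 10% | 1% | 0.1% |
| 20% | 20% | 4% | 0.8% |
| 30% | 30% | 9% | 2.7% |

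At q = 20%, taking adherence is 80% on all three regimens, while the mean longest gap over 180 days is about 3.0, 1.3 and 0.8 days (simulated).

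**Sensitivity of the gaps figure.** If half of the misses are shared across the whole day, the expected gap fraction is 0.5q + 0.5q^k. At q = 30% this gives 30%, 0.15 + 0.045 = 19.5%, and 0.15 + 0.0135 = 16.35%. The dependence on regimen shrinks but remains.

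**Arm comparison: validity.** Simulated type I error of the pooled t-test is about 5%. Chance imbalance: with 70 per arm and half the patients once daily, the SD of the difference in the once-daily share is √(2 × 0.5 × 0.5/70) = 0.085, so the 95% range is ±17 percentage points. At q = 20% (gaps 20% versus 4%), that moves the arm difference in gaps by 0.166 × 16 = ±2.7 points.

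**Arm comparison: power.** Simulation with 77 per arm and once/twice/three-times daily at 50/45/5. For timing, patients' dose-time SD is log-normal with median 2 h, and the reminder cuts it by 15%. For gaps, per-dose adherence is Beta(5, 1.5), and the reminder cuts missed doses by 25%.

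| Scenario | t-test | adjusted for frequency |
|---|---|---|
| Timing, log-SD 0.3 | 48% | 85% |
| Timing, log-SD 0.5 | 31% | 42% |
| Timing, log-SD 0.7 | 22% | 25% |
| Timing, log-SD 0.5, variability proportional to the interval | 41% | 41% |
| Gaps, independent misses | 54% | 69% |
| Gaps, half of misses shared within the day | 70% | 75% |

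**Association with exacerbation.** Cox simulations in which hazard depends on regimen and not on adherence:

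- Gaps (154 patients, half once and half twice daily, miss probability Beta(4, 16), once- versus twice-daily hazard ratio 0.5 or 2): false-positive rate about 21% or 36% unadjusted, about 4.5% with regimen in the model.
- Timing adherence (140 patients, about 29 events, hazard 1.5 to 2 times higher off once-daily dosing): 11–21% unadjusted, 4% stratified.
- Regimen unrelated to hazard (run for gaps): about 5% without adjustment.

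**The case against.** Four arguments have weight.

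First, the arms are randomised, so regimen balances in expectation and an unadjusted test of a secondary outcome is valid. This stands. A reader might infer that the arm comparisons partly measure regimen instead of behaviour. The documents do not support that: the cost is precision and chance imbalance, not bias.

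Second, the ±25% rule is a deliberate relative scale that the protocol describes as widely used. If dose-time variability shrinks in proportion to the interval, timing adherence is 96.6% on all three regimens (2 h, 1 h and 40 min against windows of 6, 3 and 2 h), and adjusting gains nothing. The documents support neither this assumption nor that of equal variability in hours. Gaps, however, have no scaling to the regimen at all.

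Third, large power gains need favourable assumptions. This also stands: with more variation between patients, or with misses that take out whole days, the gain is small. A single headline gain should not be quoted.

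Fourth, confounding of the association requires regimen to be related to exacerbation risk. A reader might infer that dosing frequency tracks drug and disease here and that spurious predictors are therefore expected. No section shows such a link, and none excludes it. The analysis is also one exploratory sentence with no stated model, so adjustment could still be added.

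**Conclusion.** The concern holds in limited form. Timing adherence, gaps and maximal gap length depend on dosing frequency for identical per-dose behaviour. Taking adherence does not. The direction follows from the definitions, assuming for timing that irregularity in hours does not shrink in proportion to the interval, and for gaps that not every miss takes out a whole day. The size rests on the assumed dose-time SD and miss pattern.

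For the randomised comparison the consequence is efficiency: from no gain to 48% versus 85% power across the scenarios tried, with type I error intact. For the association with exacerbation it is possible confounding, with false-positive rates of about 11–36% if the regimen hazard ratio is 0.5 or 1.5 to 2, and about 5% if there is no such relation. The primary arm comparison of time to next exacerbation and the sample size are untouched. This is a worthwhile, near-free improvement to secondary and exploratory analyses, not the correction of an invalid test.

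**What to change.** Add one paragraph to Statistical analysis before the arms are compared:

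- Report timing adherence, gaps and maximal gap length by baseline prescribed dosing frequency as well as overall.
- Compare arms with a linear model containing arm and baseline dosing frequency, with robust standard errors.
- Stratify or adjust the exploratory Cox models for timing adherence and gaps by baseline dosing frequency.
- Give each patient one frequency category and one score by a pre-set rule, for example a mixed category for inhalers on different frequencies, with the per-inhaler scores averaged. If inhaler-level rows are kept for the arm comparison, cluster standard errors by patient. The Cox models need one row per patient so that no exacerbation is counted twice.
- State how intervals and gap days are scored if the prescription changes during follow-up, keeping the baseline category as the covariate.

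Frequency comes from the current medication already recorded at baseline, so no new data are needed. The cost is the effort of agreeing the several-inhaler rule and a few degrees of freedom.

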The objective of this study is to investigate the adherence to inhaled medication in asthma and COPD patients with an innovative methodology using specific electronic devices, which are able to provide data about the timing of inhaler action. Moreover, we want to assess the effect of an acoustic reminder and a close supervision by a pharmacist on the adherence, course of diseases and quality of life.

METHODS AND ANALYSIS

PARTICIPANTS AND RECRUITMENT

In- and outpatients with a diagnosis of asthma bronchiale or COPD from several hospitals in the Basel region illustrated on table 1 and patients treated by pulmonologists in private practice are screened for eligibility. In addition, advertisement is made using posters, flyers, as well as on ad-screens (Cantonal Hospital Baselland Liestal and Bruderholz) including the most important information about the study. Advertisement is also placed in local newspapers.

Table 1 Recruitment locations and related recruitment types

Hospital	Location	Type of recruitment
Cantonal Hospital Baselland	Liestal, Switzerland	- Screening of hospitalized

		patients
Cantonal Hospital Baselland	Bruderholz, Switzerland	- Screening of emergency department
Claraspital	Basel, Switzerland	- Screening of DRG-lists
Clinic Barmelweid	Barmelweid, Switzerland	- Screening of DRG-lists
Gesundheitszentrum Fricktal AG	Rheinfelden, Switzerland	- Collaboration with pulmonology department
		- Collaboration with pulmonology department
		- Collaboration with pulmonology department
		- Collaboration with pulmonology department

DRG, Diagnosis Related Groups.

In- and exclusion criteria initially are checked via telephone or during hospitalizations or practice visits. Eligible patients are invited for an initial training course. Before the study start, the investigator provides written and verbal information on content and duration of the study. In case of willingness to participate, patients have to sign an informed consent.

PATIENT INCLUSION CRITERIA

- males and females aged ≥ 18 years with
- asthma- and/or COPD diagnoses and
- prescribed daily inhaled medication with
- at least one exacerbation in the previous twelve months

PATIENT EXCLUSION CRITERIA

- patients with malignancies and/or other severe diseases or
- insufficient German language
- pregnant or lactating women

Enrolment started on January 2014 and will end as soon as at least 154 individuals are included in the study.

STUDY DESIGN AND PROCEDURES

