Visits take place at baseline (T0), after two (T1), four (T2) and six months (T3). Each visit includes a spirometry (EasyOne Pro, ndd Medizintechnik AG, Zurich, Switzerland), measurement of diffusion capacity (EasyOne Pro, ndd Medizintechnik AG, Zurich, Switzerland), exhaled nitric oxide (NIOX MINO®, Aerocrine AB, Sweden) and carbon monoxide (piCO⁺ Smokerlyzer, Bedfont Scientific Ltd., Kent, UK) measurements. To detect false device applications, each patient is asked to demonstrate the inhalation technique with all prescribed devices to the investigator using a placebo device (to avoid overdosing). Moreover, participants have to fill out the COPD Assessment Test (CAT)[41], the Asthma Control Test (ACT)[42], the St. George’s Respiratory Questionnaire (SGRQ) and the Short Form (SF)-36[43, 44] to assess quality of life at baseline, after two, four and six months. To assess patients’ beliefs about the necessity of the prescribed medication and their concern about the potential adverse consequences of taking it, the Beliefs about medicines Questionnaire (BMQ) is used at baseline[45, 46]. During these visits we also obtain information about exacerbation since the previous visit.

RANDOMIZATION

After having given written informed consent eligible subjects are randomly assigned either to the intervention or to the control group. The intervention group is provided with an acoustic reminder for inhalation and receives support calls when the medication is not taken as prescribed while the control group receive no further support regarding the adherence. A randomization list with study group allocation is generated using R (RStudio®, Boston, USA). Randomization procedure is provided in block size of two. Therefore, examinations between study groups are sequent. This reduces the risk of a season effect between study groups. The patients are not aware of which group they have been randomized to (single-blinded).

CLINICAL INTERVENTIONS

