Currently, no monitoring devices exist that were specifically developed for monitoring the adherence of the newly introduced inhalation-device Ellipta®. To assess adherence in patients undergoing treatment with Ellipta® a Smartinhaler with a placebo-device is handed out and patients are instructed to trigger a puff of the placebo every time when they inhale their active treatment. This procedure allows an indirect recording of date and time actuation of the Ellipta® inhaler.

For inhalation with powder capsules (Breezhaler and HandiHaler), POEMS are used. The capsules are pre-filled for the following 2 weeks with a patient's individualized prescription plan (mostly one time daily inhalation of capsule contents). The multidose punch cards are filled manually by a pharmacist. The participants with Breezhaler and HandiHaler will receive one multidose punch card for every 2 weeks. Every time the patients break a loop for taking the capsules, date and time are recorded on a microchip, which can be read when the patients bring back the empty punch card.

DATA COLLECTION AND OUTCOME MEASURES

The primary outcome of this study is “time to next asthma or COPD exacerbation”, defined as acute-onset worsening of the patient's condition beyond day-to-day variations requiring interaction with a health care provider[48], which may occur during the index exacerbation or follow-up. Data collections about this outcome are assessed after two, four and six months (number of exacerbations since last visit with exact period of exacerbation and number of exacerbation with hospitalization). If patients are not able to give information about the time of exacerbation, treating physician is contacted.

Sociodemographic variables such as gender, civil status, age, education level and employment status are obtained by a generic questionnaire at the baseline visit. Furthermore, body mass index (BMI), smoking status, as well as pack years (py) are assessed during this visit. In addition, disease-related questions such as allergies,

comorbidities, current medication and number of exacerbations in the previous twelve months are recorded including hospitalizations and emergency department attendance.

This project focuses on the implementation of a prescribed dosing regimen. Objective adherence will be analyzed according to the following widely used definitions[49]:

- Taking adherence: (Number of puffs inhaled during 24h/number of puffs prescribed during 24h) x 100.

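### The primary Cox comparison names no stratum or baseline covariate, although diagnosis and prior-year exacerbation count are known at entry and could recover some precision

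*Combined protocol and SAP*

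**What the plan says.** All references are to the combined protocol and SAP.

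- **Endpoint** (Data Collection and Outcome Measures): "The primary outcome of this study is “time to next asthma or COPD exacerbation". Two diseases share one event definition.
- **Population** (Patient Inclusion Criteria): patients enter with "asthma- and/or COPD diagnoses and" a history of "at least one exacerbation in the previous twelve months". Patients may have both diagnoses, and the prior count starts at one and can be higher.
- **Allocation** (Randomization): "Randomization procedure is provided in block size of two". No stratification factor is given.
- **Primary comparison** (Statistical Analysis): "Time to next exacerbation is compared using the Kaplan-Meier method and Cox proportional hazard model". No stratum or baseline covariate is named.
- **Other modelling** (same section): "Associations between time to between exacerbation and independent predictors will be analyzed (taking adherence, timing adherence and gaps without" inhalation). These are measured after randomisation and belong to a separate association analysis.
- **Baseline data** (Data Collection and Outcome Measures): the "number of exacerbations in the previous twelve months are recorded" at the baseline visit.
- **Covariates in general** (Handling of Missing Data and Drop Outs): the word appears only in the reason for multiple imputation, "which is typically more efficient than complete cases analysis when covariates have missing values[56". No covariate is named.

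**The concern.** Asthma and COPD patients may exacerbate at different rates, and patients with several recent exacerbations may differ from those with one. If so, a comparison that ignores both factors gives up information. With about 30 expected events there is little to spare. Three things could be at stake: power, the size of the reported hazard ratio, and the credibility of the result if the arms happen to differ in disease mix or history. Neither the allocation nor the stated analysis deals with any of these, although the data needed are already collected.

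**Working it through.** **1. The plan's own figure.** Inputs from Calculation of Sample Size: 30% control risk, 12% intervention risk, 70 per group, one-tailed 5%, power 80%.

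- HR = ln(1 - 0.12) / ln(1 - 0.30) = ln 0.88 / ln 0.70 = 0.358, which matches the stated 0.36.
- Expected events = 70 × 0.30 + 70 × 0.12 = 21 + 8.4 = 29.4. With 77 per arm: 77 × 0.42 = 32.3.
- Freedman power = Φ(√29.4 × (1 - 0.36)/(1 + 0.36) - 1.645) = Φ(2.552 - 1.645) = Φ(0.907) = 81.8%.

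The stated 80% is therefore reproduced by a plain two-group calculation.

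**2. Precision of the HR.** SE(log HR) ≈ √(1/21 + 1/8.4) = 0.41. The expected 95% CI around 0.36 is exp(-1.022 ± 1.96 × 0.41), about 0.16 to 0.80.

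**3. Chance imbalance in a binary factor, 70 per arm.** SD of the difference = √(2p(1 - p)/70). The documents do not give the disease mix, so p is varied.

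| Prevalence p | P(difference ≥ 10 points) | P(difference ≥ 15 points) |
|---|---|---|
| 30% | 20% | 5% |
| 40% | 23% | 7% |
| 50% | 24% | 8% |

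**4. What such an imbalance does.** Assume a 50/50 mix, a 15-point imbalance and one diagnosis doubling the hazard. The crude HR is multiplied by about (0.575 + 2 × 0.425)/(0.425 + 2 × 0.575) = 1.425/1.575 = 0.905. That is 0.10 on the log scale, and 0.10/0.41 is about a quarter of one standard error.

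**5. Power with and without the factors.** The first simulation had 140 patients, blocks of two, exponential times, control risk held at 30%, treatment HR 0.358 and 3,000 trials per row. Diagnosis was split 50/50, and 40% were in a higher prior-exacerbation category. The prognostic HR shown applies to each factor. All three analyses were run on the same simulated trials.

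| Prognostic HR | One-sided 5% power: unadjusted | Stratified by diagnosis | Adjusted for both | Two-sided 5%: unadjusted to adjusted for both | Median HR: unadjusted / adjusted for both |
|---|---|---|---|---|---|
| 1.0 | 83.8% | 83.5% | 83.8% | 73.8% to 73.4% | 0.356 / 0.353 |
| 1.5 | 83.6% | 83.8% | 84.5% | 73.8% to 74.5% | 0.359 / 0.354 |
| 2 | 84.1% | 84.9% | 85.7% | 73.7% to 75.9% | 0.362 / 0.348 |
| 3 | 79.9% | 81.8% | 84.5% | 69.2% to 75.8% | 0.382 / 0.351 |

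With no treatment effect, the one-sided error was 4.3-5.5% across all analyses.

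A second simulation used the model proposed under the fix, stratified by diagnosis with the prior count as a covariate (77 per arm, two-sided 5%, 2,000 trials per scenario, true HR 0.36):

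- Weak (diagnosis HR 1.5, 1.2 per prior event): power 77.2% to 77.3%.
- Moderate (2 and 1.5): 76.4% to 78.8%.
- Strong (3 and 2): 71.6% to 79.4%, with median HR 0.397 unadjusted and 0.358 adjusted.

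A third, with 1,500 trials per scenario and 77 per arm, gave 78.1% to 78.5%, 75% to 78% and 75% to 81% for weak, moderate and strong factors. Together the gains are about 0-1, 2-3 and 5-8 points. The Monte Carlo standard error of a single power figure is about 0.7 points with 3,000 trials (√(0.84 × 0.16/3000)) and about 1.1 with 1,500.

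**The case against.** **The plan is silent on covariates; it does not specify a treatment-only model.** This stands. The imputation paragraph refers to covariates, and its reference concerns imputing covariates in Cox models, so some adjustment may have been in mind. A reader might infer that the plan commits to an unadjusted model, but the text does not say so. Silence still leaves the primary model open. Nothing in the documents suggests that the model would be chosen by its result. Even so, in the second simulation with no effect, reporting whichever of the two models was significant gave 5.4-8.0% two-sided error, against 3.8-6.1% for either model alone.

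**An unadjusted comparison of randomised arms is valid.** This stands in full. The simulated error rates are at their nominal level, and chance imbalance is part of the variation that the confidence interval already describes.

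**The gains are small and rest on assumptions.** This largely stands. The documents give no disease mix and no prognostic effects, and for weak factors the gain is close to nothing.

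**The attenuation is partly a difference between two quantities.** This also stands. A marginal HR and a conditional HR are different targets, so 0.38 against 0.35 is not plain bias.

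**The change is not free.** Patients with both diagnoses need a rule, the count needs a functional form, and about 8 intervention events would be spread over two strata. Enrolment began in January 2014 and study staff know the allocation, so a late change of primary model needs careful handling. These points limit how the fix is worded. They do not remove the reason for it.

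**Conclusion.** The point holds as a modest improvement in efficiency and pre-specification. Neither the stated allocation nor the stated primary analysis uses diagnosis or exacerbation history, although both are known at entry. The expected gain is about 0-1 points of power for weak factors, 2-3 for moderate and 5-8 for strong. In the first simulation, where neither factor mattered, adjusting for both cost at most 0.4 points.

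These sizes rest on assumed prognostic effects, an assumed disease mix, the same treatment HR in every patient, and a 30% control risk that the plan takes from COPD readmissions alone.

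Two stronger readings are tempting. One is that pooling the diseases makes the primary test biased or inflates its error rate; the calculations show no inflation, and randomisation protects the comparison. The other is that imbalance is likely to distort the HR materially. The 10% shift in step 4 needs an imbalance with a probability of about 8% or less, plus an assumed doubling of hazard, and it is still only about a quarter of one standard error.

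**What to change.** Before any comparison of outcomes by arm, add to Statistical Analysis: *The primary analysis is a Cox model for time to first exacerbation after baseline, with treatment as the effect of interest, stratified by diagnosis (asthma only versus any COPD) and adjusted for the number of exacerbations in the year before entry, entered as one term. The unadjusted Kaplan-Meier and Cox results are supportive.*

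Fix the form of the count in the same text, for example 1 versus 2 or more, or a linear count with a stated cap. Defining the stratum as any COPD places patients with both diagnoses by rule.

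The cost is a short amendment and no new data. The reported HR becomes conditional rather than marginal, and one extra coefficient is estimated from about 29-32 expected events. The set of factors should therefore stay at these two. Because the trial is ongoing and only patients are blinded, the amendment should be dated and should record that no outcome data by arm had been examined when it was made.
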